10.11.8.2.2. Blinding of Site Personnel

The study staff receiving, storing, dispensing, preparing, and administering the study interventions will be unblinded. All other study and site personnel, including the investigator and investigator staff, will be blinded to assignment of study intervention. In particular, the individuals who evaluate participant safety will be blinded. Because there are differences in physical appearance between study interventions, study interventions will be administered in a manner that prevents the participants from identifying the study intervention based on its appearance.

The PI will assign the responsibility of the unblinded dispensers/administrators to persons who will not participate in the evaluation of any study participant. To ensure adequate coverage, at least 2 unblinded dispensers/administrators will be assigned per site. Members of the study site nursing/medical staff or clinic pharmacy will fulfill these roles. Contact between the unblinded dispensers and study participants should be kept to a minimum. The investigator, study coordinator, and any site staff other than the unblinded dispensers/administrators must not be allowed to know the study intervention assigned to any study participant and must not be allowed to see the study intervention container contents.

In the event of a Quality Assurance audit, the auditor(s) will be allowed access to unblinded study intervention records at the site(s) to verify that randomization/dispensing has been done accurately.

10.11.8.2.3. Blinding of the Sponsor

All laboratory testing personnel performing serology assays will remain blinded to study intervention assigned/received throughout the study. The following sponsor/Pfizer staff, who will have no part in the blinded conduct of the study, will be unblinded (further details will be provided in a data blinding plan):

- Those study team members who are involved in ensuring that protocol requirements for study intervention preparation, handling, allocation, and administration are fulfilled at the site will be unblinded for the duration of the study (eg, unblinded study manager, unblinded clinical research associate).
- Unblinded clinician(s), who are not direct members of the study team and will not participate in any other study-related activities, will review unblinded protocol deviations.
- An unblinded team will support interactions with and analyses for the IRC (see [Section 10.1.5](#)). This team comprises a statistician, programmer(s), a clinical scientist, and a medical monitor.

When the 1-month analysis has been performed, and when directed by the sponsor (anticipated to be between Visit A102 and Visit A103), participants may be unblinded to confirm the vaccine received. The study team will also become unblinded to the participant's study intervention allocation at this time.

10.11.8.2.4. Breaking the Blind

See [Section 6.4.4](#).

10.11.8.3. Study Intervention Compliance

See [Section 6.5](#).

10.11.8.4. Dose Modification

NA.

10.11.8.5. Continued Access to Study Intervention After the End of the Study

See [Section 6.7](#).

10.11.8.6. Treatment of Overdose

See [Section 6.8](#).

10.11.8.7. Prior and Concomitant Therapy

For Substudy A, the following concomitant medications and vaccinations will be recorded in the CRF:

- Prior receipt of any COVID-19 vaccine.
- Influenza vaccine*, if received during the 12 months prior to enrollment.
 - *Include product name and date of administration.
- Any vaccinations received from 28 days prior to study enrollment until the last visit (A103).
- Prohibited medications listed in Section 10.11.8.7.1, if taken, will be recorded and include start and stop dates, name of the medication, dose, unit, route, and frequency.

10.11.8.7.1. Prohibited During the Study

Receipt of the following vaccines and medications during the time periods listed below may exclude a participant from the per-protocol analysis from that point onward; however, it is anticipated that the participant would not be withdrawn from the study (see [Section 7](#)).

Medications should not be withheld if required for a participant's medical care.

- Unless considered medically necessary, no vaccines other than study intervention should be administered within 28 days before and 28 days after study vaccination at Visit 1.
- Licensed or nonstudy investigational coronavirus vaccine from enrollment through 31 August 2023.
- Licensed or nonstudy investigational influenza vaccine from enrollment through 31 August 2023.
- Licensed or nonstudy investigational RSV vaccine from enrollment through 31 August 2023.
- Receipt of chronic systemic treatment with known immunosuppressant medications, or radiotherapy, within 60 days before enrollment through conclusion of the study is prohibited.
- Receipt of systemic corticosteroids (≥ 20 mg/day of prednisone or equivalent) for ≥ 14 days is prohibited from 28 days prior to enrollment through 28 days after administration of the study intervention.
- Receipt of blood/plasma products, immunoglobulins, or monoclonal antibodies, from 60 days before study intervention administration through conclusion of the study.
- Prophylactic antipyretics and other pain medication to prevent symptoms associated with study intervention administration are not permitted. However, if a participant is taking a medication for another condition, even if it may have antipyretic or pain-relieving properties, it should not be withheld prior to study vaccination.

10.11.8.7.2. Permitted During the Study

- Medication other than that described as prohibited in [Section 10.11.8.7.1](#) required for treatment of preexisting conditions or acute illness is permitted.
- Inhaled, topical, or localized injections of corticosteroids (eg, intra-articular or intrabursal administration) are permitted.

10.11.9. Discontinuation of Substudy A Intervention and Participant Discontinuation/Withdrawal

See [Section 7](#).

10.11.10. Substudy A Assessments and Procedures

For Substudy A, the minimal blood sampling volume for all individual participants in this study is approximately 100 mL.

For all participants in Substudy A, other additional blood samples may be taken for safety assessments, provided the total volume taken during the study does not exceed 550 mL during any period of 60 consecutive days.

10.11.10.1. Immunogenicity Assessments

Samples will be collected at time points as specified in [Section 10.11.3](#) from all applicable participants, and the following assays will be performed:

- HAI titers for the matched seasonal strains (2×A, 2×B) recommended by WHO for Groups 1, 5, and 7.
- SARS-CoV-2 neutralization assay (reference strain) for Groups 1, 2, 3, 6, and 7.
- SARS-CoV-2 neutralization assays (Omicron BA.4, Omicron BA.5; other variants, including other Omicron sublineages, may also be evaluated) for Groups 1, 2, 3, 6, and 7.
- RSV A and RSV B serum NTs for Groups 1, 2, 4, 6, and 7.

10.11.10.2. N-Binding Antibody Test

The N-binding antibody test will be performed by the central laboratory on each blood sample to establish prior exposure to SARS-CoV-2 up to each time point.

10.11.10.3. Biological Samples

See [Section 8.2.1](#).

10.11.10.4. Safety Assessments

See [Section 8.3](#).

10.11.10.5. Stopping Rules

The following stopping rules are in place for Substudy A participants, based on review of AEs, ECG, and laboratory data, and apply to study vaccination (Day 1) through Day 28. These data will be monitored on an ongoing basis by the investigator (or medically qualified designee) and sponsor in order to promptly identify and flag any event that potentially contributes to a stopping rule. In the event that sponsor personnel confirm that a stopping rule is met, the following actions will commence:

- The IRC will review all appropriate data.
 - The stopping rule will PAUSE randomization and any further study intervention administration.

- For all participants already vaccinated, all other routine study conduct activities, including ongoing data entry, reporting of AEs, participant e-diary completion, blood sample collection, and participant follow-up, will continue during the pause.

A stopping rule is met if any of the following criteria occur within 28 days after study intervention administration.

Stopping Rule Criteria:

If any participant vaccinated with the combined RSVpreF and bivalent BNT162b2 (original/Omi BA.4/BA.5) vaccine [RSVpreF+BNT162b2] develops:

1. A new ECG abnormality that a cardiologist judges consistent with probable or possible myocarditis or pericarditis, including:
 - Sustained atrial or ventricular arrhythmias
 - Second-degree Mobitz Type II or worse AV block, new bundle branch block
 - Diffuse ST-segment elevation or PR-segment inversion, compatible with pericarditis
2. An abnormal troponin value that is confirmed abnormal on repeat testing, assessed as related to study intervention by the investigator.
3. If ≥ 1 participant vaccinated with any [RSVpreF+BNT162b2] combination develops confirmed myocarditis or pericarditis.
4. If any participant vaccinated with any [RSVpreF+BNT162b2] combination dies.

A charter for the IRC will be prepared and finalized before the first participant provides consent.

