8.3.4.2. Local Reactions

During the reactogenicity e-diary reporting period, participants will be asked to assess redness, swelling, and pain at the injection site and to record the symptoms in the reactogenicity e-diary. In Substudy A, local reactions will be assessed at the injection site on the right arm.

If a local reaction persists beyond the end of the reactogenicity e-diary period following vaccination, the participant will be requested to report that information. The investigator will enter this additional information in the CRF.

Participants will be provided with a measuring device. Redness and swelling will be measured and recorded in measuring device units (range: 1 to 21) and then categorized during analysis as absent, mild, moderate, or severe based on the grading scale in Table 1. Measuring device units can be converted to centimeters according to the following formula: 1 measuring device unit = 0.5 cm. Pain at the injection site will be assessed by the participant as absent, mild, moderate, or severe according to the grading scale in Table 1.

If a Grade 3 local reaction is reported in the reactogenicity e-diary, a telephone contact should occur to ascertain further details and determine whether a site visit is clinically indicated. Only an investigator or medically qualified person is able to classify a participant's local reaction as Grade 4. If a participant experiences a confirmed Grade 4 local reaction, the investigator must immediately notify the sponsor.

Table 1. Local Reaction Grading Scale

	Mild (Grade 1)	Moderate (Grade 2)	Severe (Grade 3)	Potentially Life-Threatening (Grade 4)
Pain at the injection site	Does not interfere with activity	Interferes with activity	Prevents daily activity	Emergency room visit or hospitalization for severe pain
Redness	>2.0 cm to 5.0 cm (5 to 10 measuring device units)	>5.0 cm to 10.0 cm (11 to 20 measuring device units)	>10 cm (\geq 21 measuring device units)	Necrosis or exfoliative dermatitis
Swelling	>2.0 cm to 5.0 cm (5 to 10 measuring device units)	>5.0 cm to 10.0 cm (11 to 20 measuring device units)	>10 cm (\geq 21 measuring device units)	Necrosis

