8.3.4.3. Systemic Events

During the reactogenicity e-diary reporting period, participants will be asked to assess vomiting, diarrhea, headache, fatigue, chills, new or worsened muscle pain, and new or worsened joint pain and to record the symptoms in the reactogenicity e-diary. The symptoms will be assessed by the participant as absent, mild, moderate, or severe according to the grading scale in [Table 2](#).

If a systemic event persists beyond the end of the reactogenicity e-diary period following vaccination, the participant will be requested to report that information. The investigator will enter this additional information in the CRF.

If a Grade 3 systemic event is reported in the reactogenicity e-diary, a telephone contact should occur to ascertain further details and determine whether a site visit is clinically indicated. Only an investigator or medically qualified person is able to classify a participant's systemic event as Grade 4. If a participant experiences a confirmed Grade 4 systemic event, the investigator must immediately notify the sponsor and, if it is determined

to be related to the administration of the study intervention, further vaccinations will be discontinued in that participant.

Table 2. Systemic Event Grading Scale

	Mild (Grade 1)	Moderate (Grade 2)	Severe (Grade 3)	Potentially Life-Threatening (Grade 4)
Vomiting	1-2 times in 24 hours	>2 times in 24 hours	Requires IV hydration	Emergency room visit or hospitalization for hypotensive shock
Diarrhea	2 to 3 loose stools in 24 hours	4 to 5 loose stools in 24 hours	6 or more loose stools in 24 hours	Emergency room visit or hospitalization for severe diarrhea
Headache	Does not interfere with activity	Some interference with activity	Prevents daily routine activity	Emergency room visit or hospitalization for severe headache
Fatigue/tiredness	Does not interfere with activity	Some interference with activity	Prevents daily routine activity	Emergency room visit or hospitalization for severe fatigue
Chills	Does not interfere with activity	Some interference with activity	Prevents daily routine activity	Emergency room visit or hospitalization for severe chills
New or worsened muscle pain	Does not interfere with activity	Some interference with activity	Prevents daily routine activity	Emergency room visit or hospitalization for severe new or worsened muscle pain

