10.11.6. Substudy A Design

10.11.6.1. Overall Design

This is a Phase 1/2 randomized, parallel-group, observer-blinded substudy to describe the safety, tolerability, and immunogenicity of a combined RSVpreF and bivalent BNT162b2 (original/Omi BA.4/BA.5) vaccine [RSVpreF+BNT162b2], administered concomitantly with a seasonal influenza vaccine or administered alone. Approximately 1050 healthy participants ≥ 65 years of age will be enrolled in Substudy A.

Note: "Enrolled" means a participant's, or their legally authorized representative's, agreement to participate in a clinical study following completion of the informed consent process.

Randomization will be conducted across 2 enrollment strata (see Table 4).

Table 4. Substudy A Enrollment Strata

Enrollment Stratum	Total Number of Participants	Number of Participants per Vaccine Group	Vaccine Group Number	Vaccine Group Description
1	750	150	1	[RSVpreF+BNT162b2] administered concurrently in the opposite arm to licensed QIV
		150	2	[RSVpreF+BNT162b2] administered concurrently in the opposite arm to placebo
		150	3	Bivalent BNT162b2 administered concurrently in the opposite arm to placebo
		150	4	RSVpreF administered concurrently in the opposite arm to placebo
		150	5	Licensed QIV administered concurrently in the opposite arm to placebo
2	300	150	6	RSVpreF and bivalent BNT162b2 (2 injections in the same arm) coadministered concurrently in the opposite arm to placebo
		150	7	RSVpreF and bivalent BNT162b2 (2 injections in the same arm) coadministered concurrently in the opposite arm to QIV

All participants will be asked to complete a reactogenicity e-diary for 7 days following vaccination. Blood samples of approximately 50 mL will be collected for immunogenicity assessments prior to vaccination at Visit A101 and 1 month after vaccination (Visit A102).

E-diary data from Day 1 through Day 3 for the first 50 participants in Groups 1 to 5, and the first 20 participants in Groups 6 and 7, will be evaluated prior to enrollment of the remaining participants in each group.

AEs and SAEs will be collected from the signing of informed consent through Visit A102 (1-month follow-up visit). SAEs will be collected from the signing of informed consent through Visit A103 (6-month telephone contact).

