10.11.8.1.4. Allocation to Study Intervention

See [Section 6.3](#).

Allocation of study intervention at Visit A101 in Substudy A will be conducted via the IRT.

E-diary data from Day 1 through Day 3 for the first 50 participants in Groups 1 to 5, and the first 20 participants in Groups 6 and 7, will be evaluated prior to enrollment of the remaining participants in each group. Initial enrollment will be controlled through the IRT system to manage this approach.

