3.1.2.1.2. Maximum Severity of Local Reactions Within 7 Days After Vaccination

The grading of local reactions is listed in Table 4.

Table 4. Grading Scale for Local Reactions

	Mild Grade 1	Moderate Grade 2	Severe Grade 3 ^a	Grade 4 ^b
Redness	Mild grading from the e-diary per Table 1 in the protocol or mild from the AE CRF	Moderate grading from the e-diary per Table 1 in the protocol or moderate from the AE CRF	Severe grading from the e-diary per Table 1 in the protocol or severe from the AE CRF	Necrosis or exfoliative dermatitis
Swelling	Mild grading from the e-diary per Table 1 in the protocol or mild from the AE CRF	Moderate grading from the e-diary per Table 1 in the protocol or moderate from the AE CRF	Severe grading from the e-diary per Table 1 in the protocol or severe from the AE CRF	Necrosis
Pain (at the injection site)	Does not interfere with activity (mild from the e-diary or AE CRF)	Interferes with activity (moderate from the e-diary or AE CRF)	Prevents daily activity (severe from the e-diary or AE CRF)	Emergency room visit or hospitalization for severe pain at the injection site

- a. The maximum reaction size in measuring device units is 21 (10.5 cm). Any reaction size >21 measuring device units is recorded as a number that is >20 (eg, 21) in the e-diary.
- b. Grade 4 assessments should be made by the investigator using the AE severity grading scale. The assessment will be collected on the AE CRF and thus not reported from the e-diary.

The following variables are derived for each participant included in the reactogenicity analysis:

1. Maximum severity of each local reaction item on any day (Day 1 through Day 7) after vaccination.

The maximum severity (highest grading) of each local reaction within 7 days after vaccination will be derived. The maximum severity will be derived as follows:

= Missing, if values are missing for all days (Days 1-7);

- = 0, if the participant reports all reactions as “no” or a combination of missing and “no” for all days (Days 1-7);
- = *Highest grade* (maximum severity) within 7 days after vaccination (either from the e-diary or in the AE CRF), if the answer is not “no” for at least 1 day.

2. Maximum severity of any local reaction on any day (Day 1 through Day 7) after vaccination.

The maximum severity for any local reaction after vaccination will be derived as follows:

- = Missing, if values are missing for all days (Days 1-7) across all 3 local reactions;

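### The protocol and SAP contain no reaction-based pause rule for the first-in-human combination, so a related Grade 4 reaction that is neither fatal nor cardiac halts dosing only at someone's discretion

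*Protocol*

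**What the plan says.** **Stopping rules (Protocol 10.11.10.5).** The section introduces its list with "A stopping rule is met if any of the following criteria occur within 28 days after study intervention administration". The four criteria concern recipients of [RSVpreF+BNT162b2] only:

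1. a new ECG abnormality that a cardiologist finds consistent with myocarditis or pericarditis;
2. "An abnormal troponin value that is confirmed abnormal on repeat testing, assessed as related to study intervention by the investigator";
3. confirmed myocarditis or pericarditis;
4. death.

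Meeting any one of them pauses randomization and dosing and sends the data to the IRC.

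**Grade 4 reactions (Protocol 8.3.4.2 to 8.3.4.4).** For local reactions: "If a participant experiences a confirmed Grade 4 local reaction, the investigator must immediately notify the sponsor". For a confirmed, related systemic event the sponsor is also notified and "further vaccinations will be discontinued in that participant". Fever above 40.0°C is handled in the same way. Protocol 7.1 treats discontinuation of study intervention as not applicable because each participant is vaccinated on one occasion.

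**Early review (Protocol 10.11.6.1 and 10.11.8.1.4).** The Day 1–3 e-diary entries of an initial set of participants (50 for Groups 1 to 5, 20 for Groups 6 and 7) are looked at first. Section 10.11.6.1 says that they "will be evaluated prior to enrollment of the remaining participants in each group". Section 10.11.8.1.4 adds how the order is enforced: "Initial enrollment will be controlled through the IRT system to manage this approach". The amendment history (10.12) gives the absence of earlier human experience with the combination as the reason for this step.

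**Where Grade 4 is recorded.** For systemic events, "The symptoms will be assessed by the participant as absent, mild, moderate, or severe". For Grade 4 local reactions, SAP Table 4 (3.1.2.1.2), footnote b, says "The assessment will be collected on the AE CRF and thus not reported from the e-diary". Protocol 10.11.10.7.4 requires telephone contact or a site visit to confirm any suspected Grade 4 event that appears in the e-diary.

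**The concern.** The list of triggers is closed, and no local reaction, systemic event or fever is on it. One repeat-confirmed, related troponin value in one combination recipient pauses dosing in every group. One confirmed, related reaction in the protocol's highest grade does not, unless it is fatal or comes with a qualifying cardiac finding. The action the protocol does attach to a related Grade 4 systemic event or fever is directed at that participant's later doses, and there are none.

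Tolerability of the combination is a primary objective, and the early review exists because nobody had received the combination before. After a severe related reaction, the written plan leaves the decision to continue dosing other participants to judgment made once the event is known. For cardiac findings the same protocol did not rely on judgment alone.

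**Working it through.** The plan states no figure on this point, so there is none to reproduce. The check is a comparison of text followed by three short calculations.

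**1. Consequence of a single event in a combination recipient**

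| Event | Stated consequence | Pauses dosing of others? |
|---|---|---|
| Myocarditis- or pericarditis-type ECG change | Stopping rule 1 | Yes |
| Repeat-confirmed, related troponin abnormality | Stopping rule 2 | Yes |
| Confirmed myocarditis or pericarditis | Stopping rule 3 | Yes |
| Death, including a fatal reaction | Stopping rule 4 | Yes |
| Grade 4 local reaction, nonfatal and noncardiac | Sponsor notified (8.3.4.2) | Not by rule |
| Related Grade 4 systemic event, nonfatal and noncardiac | Sponsor notified; no further vaccination of that participant (8.3.4.3) | Not by rule |
| Related fever above 40.0°C, nonfatal and noncardiac | Same (8.3.4.4) | Not by rule |

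The SAP adds no pause rule.

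**2. Combination recipients dosed after the early review**

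Groups 1 and 2 receive the combination: 2 × 150 = 300. The text does not settle whether the first 50 is a total over Groups 1 to 5 or a number per group. The amendment history refers to the first 50 in Stratum 1, which favors a total.

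- Total, equal allocation assumed: 50 × 2/5 = 20 before the review; 300 − 20 = 280 after it (93%).
- Per group: 2 × 50 = 100 before; 300 − 100 = 200 after (67%).

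**3. What a clean early review would exclude**

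With 0 events in n, the one-sided 95% upper bound on the true rate is 1 − 0.05^(1/n).

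- n = 20: 1 − 0.05^(1/20) = 13.9%.
- n = 100: 1 − 0.05^(1/100) = 3.0%.

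On either reading, a clean review says little about uncommon reactions, and it does not cover the 200 to 280 recipients who follow.

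**4. How often a single-event Grade 4 rule would pause the study**

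The documents give no related Grade 4 rate, so the rates p below are assumptions. P(at least one in 300) = 1 − (1 − p)^300.

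| Assumed p | Chance of at least one pause |
|---|---|
| 0.05% | 14% |
| 0.1% | 26% |
| 0.5% | 78% |
| 1% | 95% |

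**The case against.** **Protection exists without a rule.** Grade 4 reactions reach the sponsor immediately, investigators and sponsor clinicians can see e-diary data at all times (8.3.4), and SAEs are reported within 24 hours. The sponsor may terminate the study at its discretion (10.1.10), and the IRC monitors safety under a charter whose listed duties are only a minimum (10.1.5.1). All of this stands. A reader might infer that dosing could not be halted after such a reaction, or that no criterion exists anywhere. The documents do not support either: a discretionary hold is available, and the charter, which was not seen, may contain a criterion.

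**The e-diary is not blind to Grade 4.** Participants grade symptoms only as far as severe, and SAP Table 4 places Grade 4 local reactions on the AE CRF. From this a reader might infer that the Day 1–3 review would miss Grade 4 events. That goes too far. Under 10.11.10.7.4 a suspected Grade 4 entry leads to confirmation, a Grade 3 entry prompts a telephone contact, and temperature readings can themselves exceed 40.0°C. The SAP footnote concerns the source of analysis data. What remains is narrower: confirmation is recorded outside the e-diary, and the review is described as using e-diary data.

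**The early review is itself a hold.** The IRT enforces it and it needs no trigger. Its lack of a written threshold is mostly missing detail and would not carry this point alone. It does not reach later recipients.

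**Grade 4 is broader than it sounds.** In Protocol Tables 1 and 2 it includes an emergency room visit for severe pain or fatigue. In adults aged 65 or older, one such related visit would pause all seven groups. This is a real cost of the fix.

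**Context and timing.** Both components are given at established doses, and cardiac-focused rules fit the known myocarditis risk of BNT162b2. Past-tense wording in Protocol 2.1 and 2.2.1 suggests that Substudy A dosing may already be over, although enrollment status is not stated. If it is over, a new rule changes nothing, and only the criterion actually applied can be documented.

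**Conclusion.** The point holds for the protocol and SAP as written. No criterion in 10.11.10.5 is met by a nonfatal, noncardiac reaction of any grade, and the one further action attached to a related Grade 4 systemic event or fever has no effect in a single-dose study. That is more than missing detail, because the protocol accepts single-event pauses for troponin and ECG findings and gives no reason for treating reactions differently.

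Between 200 and 280 of the 300 combination recipients are dosed after the only built-in reactogenicity hold. The 280 (and the 13.9% bound) require the first 50 to be a total with equal allocation; the per-group reading gives 200 (and 3.0%). These counts describe who falls outside the early review. They should not be read as counts of unprotected participants, since discretionary monitoring continues throughout.

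The change should be made, but it is not critical to the trial's validity. Confidence is medium because the charter was not seen and the related Grade 4 rate is unknown.

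**What to change.** 1. **Protocol 10.11.10.5:** add a fifth criterion. Any investigator-confirmed, related Grade 4 local reaction, systemic event or fever above 40.0°C within the e-diary period in a [RSVpreF+BNT162b2] recipient pauses randomization and dosing pending IRC review. If the IRC charter already holds such a rule, cite it there instead.
2. **Protocol 10.11.6.1:** state that the Day 1–3 review includes confirmed Grade 4 events from the AE CRF as well as e-diary data, and that enrollment stays closed if the fifth criterion is met.

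The cost is wording in two sections and the chance of pausing for an isolated event. At assumed related rates of 0.05% to 0.1% a pause is possible but not likely (14% to 26%); at 0.5% to 1% it is probable (78% to 95%). The documents do not say how long a pause would last. It leads to IRC review and does not by itself end the study.
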